12.6 Analysis of Secondary Endpoint: Symptomatic skeletal-related events (SSE)

Time to first occurrence of SSE will be defined as the time from randomisation to documentation of any of the following (whichever occurs first) + 1 day:

- Use of external beam radiation therapy to relieve bone pain
- Occurrence of new symptomatic pathological bone fractures that may be vertebral or non-vertebral. Asymptomatic compression fractures detected by radiology review only will not be considered a SSE.
- Spinal cord compression
- Change in antineoplastic therapy to treat bone pain
- Surgical intervention to treat bone pain

Adverse event, concomitant medication, concomitant treatment, or survival follow-up CRFs and the participant's medical record will be the source of these findings and presented as categorical data. Patients who do not experience a SSE will be censored on the date on which they were last known to be event-free. Patients with no data after randomisation will be censored at the date of randomisation + 1 day. The Kaplan-Meier method will be used to estimate the median time to SSE for each group and a log-rank test will be used to determine if there is a statistically significant difference in the time to SSE between the two groups. Cox-proportional hazard regression will be used to estimate the magnitude of the difference between groups and adjust for stratification factors and possible confounding factors.

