12.2 Power and Sample Size for Primary Endpoint

This is a 1:1 randomised controlled trial in men with MCRPC. Registered and eligible participants will be

randomised with equal probability to one of two intervention regimens: supervised exercise for 12 cycles tapering to self-management for 12 cycles with psychosocial support or psychosocial support alone. We will stratify by whether the men are on active therapy or not at the time of registration (yes/no) and study site. A total of 866 men will enrol in this study to ensure at least 412 men evaluable for OS in each arm.

Null hypothesis (H_0)= There is no difference in OS between patients randomised to the exercise intervention plus psychosocial support vs psychosocial support alone.

Alternate hypothesis (H_A) = There is a difference in OS between patients randomised to the exercise intervention plus psychosocial support vs psychosocial support alone.

Considering a total enrolment period of 36-months and minimum 36 months follow-up for each patient after enrolment; assuming survival time follows an exponential distribution; and assuming a median OS survival of 33.5 months in the control arm, the sample size required to detect a hazard ratio (HR) of 0.78 with 80% power at significance level of 0.05 is 824, 412 men in each arm. Accounting for up to 5% of patients with missing data on OS, we aim to enrol 866 men. If we consider non-compliance of 10% in the intervention arm, which equates to 371 patients in the intervention arm who are compliant, this provides 77.7% power to detect an HR of 0.78, when comparing the 371 compliant patients with the 412 patients in the control arm at the significance level of 0.05.

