12.4 Analysis of Primary Endpoint

The primary endpoint for the study is OS (defined in Section 10). An intent-to-treat approach will be used to analyse OS. Patients alive at the end of follow-up will be censored on the date of last contact (or, if no contact after the baseline visit, at the date of randomisation + 1 day). Kaplan-Meier methods will be used to estimate the median OS for each treatment arm as well as the 1-year, 2-year, and 3-year OS rates and corresponding 95% confidence intervals. A two-sided log-rank test, stratified by treatment status (on treatment Y/N) and study site, will be used to assess the effect of the intervention. Un-stratified log-rank tests will be examined as sensitivity analyses. Cox proportional-hazard regression models will be used to estimate the hazard ratio and its 95% confidence interval to quantify the effect of the intervention on OS, adjusting for stratification factor(s). First, the base model will be evaluated and then other potential confounding factors will be considered. We will also conduct secondary analyses with consideration for non-compliance and the number of supervised sessions completed.

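### The per-arm Kaplan-Meier median time to first SSE treats death as ordinary censoring, so it comes too early for the men actually followed; cumulative incidence should replace it

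*Combined protocol and SAP*

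**What the plan says.** Section 12.6 (the endpoint is defined identically in Section 11.2) lists five components of a first SSE: radiotherapy for bone pain, symptomatic pathological fracture, cord compression, change of antineoplastic therapy for bone pain, and surgery for bone pain. Death is not one of them. The censoring rule is: "Patients who do not experience a SSE will be censored on the date on which they were last known to be event-free". It does not mention death, but a man who dies without an SSE falls under it. Section 12.5 takes the same line openly for progression-free survival, where death is a censoring date.

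The estimators follow: "The Kaplan-Meier method will be used to estimate the median time to SSE for each group and a log-rank test will be used" to compare the groups, and "Cox-proportional hazard regression will be used to estimate the magnitude of the difference between groups". The protocol nowhere mentions competing risks, cumulative incidence, or a composite of SSE or death.

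**The concern.** A man who has died cannot have a later SSE. Kaplan-Meier treats a censored man as still at risk of the event after he leaves observation. When death is the reason for leaving, the estimate refers to a setting in which nobody dies. One minus the Kaplan-Meier estimate is then never below the proportion of men who have actually had an SSE, and the median is never later than the true one. The direction of the error is certain.

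Time to first SSE is a stated secondary objective (Section 2.3), and Section 13.2 lists pathological fracture among the expected adverse events of an exercise programme in men with bone metastases. A reader will take the median as the time by which half of each arm had a skeletal event. Under the planned method it is not.

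**Working it through.** **1. How much death the plan expects.** Inputs from Sections 12.2 and 12.4: control median OS 33.5 months ("assuming a median OS survival of 33.5 months in the control arm"), exponential survival, HR 0.78, 80% power, two-sided 0.05, 1:1 allocation, 36 months of enrolment and at least 36 months of follow-up.

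- Required deaths (Schoenfeld): 4 × (1.960 + 0.842)² / (ln 0.78)² = 509.
- Control hazard: ln 2 / 33.5 = 0.02069 per month. Exercise: 0.78 × 0.02069 = 0.01614.
- Probability of death with uniform accrual over A = 36 and minimum follow-up F = 36: 1 − [exp(−λF) − exp(−λ(A+F))] / (λA). This gives 66.5% in control, 57.6% in exercise, 62.0% on average.
- Sample size: 509 / 0.620 = 821, against the stated 824. The plan's figure is reproduced.

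So Section 12.2 implies about 62% deaths (509/824 = 61.8%). This is derived, not printed, and counts all deaths. With the 60-month enrolment in the synopsis the same formula gives 68.5%; the two enrolment periods need reconciling.

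**2. Which deaths compete.** Only deaths before a first SSE do. An illness-death simulation held control median OS at 33.5 months, set the Kaplan-Meier SSE median at 20 to 60 months, and made mortality 1 to 3 times as high after an SSE as before. About 24% to 52% of control men died without an SSE by cut-off.

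**3. Size of the distortion.** The documents give neither an SSE rate nor a rate of death without SSE, so both are assumed. Let s be the SSE hazard and d the hazard of death before SSE, both constant, with d = c × 0.02069.

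- One minus Kaplan-Meier at t: 1 − exp(−s t)
- Cumulative incidence at t: s/(s+d) × [1 − exp(−(s+d) t)]
- Proportion who ever have an SSE: s/(s+d)

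A Kaplan-Meier risk of 35% at 36 months gives s = −ln(0.65)/36 = 0.01197 and a Kaplan-Meier median of 57.9 months. A risk of 50% gives s = ln 2/36 = 0.01925 and a median of 36 months.

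| Kaplan-Meier risk at 36 months | c | Cumulative incidence at 36 months | Ratio | Cumulative incidence at the Kaplan-Meier median | Ever have an SSE |
|---|---|---|---|---|---|
| 35% | 0.5 | 29.6% | 1.18 | 38.9% | 53.6% |
| 35% | 0.75 | 27.4% | 1.28 | 34.7% | 43.5% |
| 35% | 1.0 | 25.3% | 1.38 | 31.1% | 36.6% |
| 50% | 0.5 | 42.6% | 1.17 | 42.6% | 65.0% |
| 50% | 0.75 | 39.5% | 1.26 | 39.5% | 55.4% |
| 50% | 1.0 | 36.8% | 1.36 | 36.8% | 48.2% |

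In these cases 31% to 43% of men, not 50%, have had an SSE at the Kaplan-Meier median. The value c = 1.0 is an upper bound: Section 1.4 associates SSE with higher mortality, so the hazard before an SSE should lie below the overall one.

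**4. When half is never reached.** s/(s+d) is below 50% when s < d, that is, when the Kaplan-Meier median exceeds 33.5/c months: 33.5 months at c = 1.0 and 67 months at c = 0.5. Maximum follow-up under Section 12.2 is 36 + 36 = 72 months, so such a median could still be reported.

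**5. Effect on the comparison of arms.** Take the same SSE hazard in both arms (s = 0.01925), c = 1.0 in control, and a ratio of 0.78 for death before SSE. The Kaplan-Meier curves coincide. Cumulative incidence at 36 months is 0.01925/0.03994 × 0.7626 = 36.8% in control and 0.01925/0.03539 × 0.7203 = 39.2% in exercise. Death without SSE is 39.5% against 32.9%.

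**The case against.** The strongest reply is that the inference is sound and only a descriptive summary is at fault. That stands. With death censored, the log-rank test and Cox model validly compare cause-specific SSE hazards. A reader might infer that the SSE comparison between arms is invalid; it is not. No decision rule uses the SSE median either, since the interim analyses in Section 12.12 concern fitness measures, OS and accrual.

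Three further inferences go beyond the documents.

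- *That the trial will publish inflated yearly SSE risks.* Section 12.6 commits only to a median, unlike Sections 12.4 and 12.5, which plan 1-, 2- and 3-year rates. The 36-month figures above show the size of the distortion; they are not planned outputs.
- *That 62% of men are lost to the competing event.* That figure includes deaths after an SSE.
- *That the reported median will be one most men never reach.* This depends on an unstated SSE rate. In three of the six cases in the table more than half the men eventually have an SSE.

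It can also be said that skeletal safety is visible elsewhere: Section 12.6 also presents the SSE findings as categorical data, and Section 13.7 compares adverse event percentages by arm. This helps in part, but adverse event collection stops 28 days after Cycle 24, and simple counts do not account for differing follow-up.

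Finally, cumulative incidence has a drawback of its own. If exercise prolongs life and leaves the SSE hazard unchanged, the exercise arm shows somewhat more SSEs (39% against 37% in step 5). That is a true description, but read alone it could pass for harm. The fix has to guard against this.

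**Conclusion.** The point holds as a fault in the descriptive summary. Following Section 12.6 as written gives a per-arm median, and any Kaplan-Meier curve shown with it, that is too early for the men followed. The direction does not depend on any assumption. The size does: for death hazards before SSE of 0.5 to 1.0 times the planned control OS hazard, with constant hazards, the Kaplan-Meier 36-month risk is overstated by a factor of about 1.2 to 1.4 in the cases shown, with the top of that range a limiting case. Whether the median is one that half the men never reach cannot be settled from the documents. The hazard comparison, the primary OS analysis and the sample size are unaffected. The change is worth making because the remedy is simple and uses data already planned.

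**What to change.** In Section 12.6:

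- Replace the Kaplan-Meier median with the Aalen-Johansen cumulative incidence of SSE by arm at 1, 2 and 3 years, with 95% confidence intervals and death without SSE as the competing event.
- Keep the log-rank test and Cox model, and label both as comparisons of cause-specific hazards.
- Show the cumulative incidence of death without SSE beside that of SSE, together with the cause-specific hazard ratio, so that a higher SSE incidence arising from longer survival is not misread.
- Add SSE-free survival (SSE or death, whichever comes first) as a supportive analysis.

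Survival and SSE status are already collected every six cycles on treatment and twice yearly afterwards (Table 1, Section 5.5.12), and the methods are in standard software. The cost is a few sentences of text and some programming. Because Section 12.6 is protocol text, a change there needs the amendment approvals in Section 17.3, and can be bundled with the next amendment.

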4.4 Randomisation

After SCC approval, patients will be randomised in a 1:1 ratio to intervention (Supervised Exercise/SE) group or control (Self-directed Exercise/SDE) group, stratifying by treatment status at time of randomisation and study site. Randomisation will be performed through the study database but maintaining concealment from patients and recruiting staff, upon which time a Study ID will be assigned to the subject.

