4.5 Stratification

Patients will be stratified by study site and treatment status at the time of registration: 1) Patients who are treatment naïve or stable on Abiraterone/Enzalutamide/Apalutamide or 2) Patients who are on/received first line chemo OR progressing on first line Abiraterone/Enzalutamide/Apalutamide. Patients treated with radium-223 will need medical monitoring review for correct stratification placement. Previous and/or concurrent treatment with other anti-cancer therapies is permitted. Patients who have previously received sipuleucel-t, meet study eligibility, and are not on the treatments listed above, are not considered on treatment. Patients

receiving experimental treatment with non-approved drugs at the time of enrolment are not eligible. Patients receiving treatment with combinations of approved drugs are eligible, provided documentation and clearance by the SCC.

Allocation within strata will be carried out using blocked randomisation in random blocks of 2, 4, or 6.

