12.5 Analysis of Secondary Endpoint: Progression-free Survival

PFS will be defined as the time from randomisation to the date of disease progression (defined in Section 11) + 1 day. Patients who have not progressed at the time of the analysis will be censored on the last date of contact OR death, whichever comes first. Patients with no data after randomisation will be censored on the day of randomisation + 1 day. An intent-to-treat approach will be used to analyse PFS. A two-sided log-rank test, stratified by treatment status at registration, will be used to assess the effect of the intervention. Kaplan-Meier methods will be used to estimate median PFS for each treatment arm and the 1-year, 2-year, and 3-year PFS rates and corresponding 95% confidence intervals. Cox proportional-hazard models will be used to assess the magnitude of the effect of the intervention, adjusting for stratification factors and other potential confounding factors.

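### The SSE log-rank test names neither randomisation factor and the PFS test omits site, unlike the OS test; if these factors are prognostic, both secondary tests are conservative and lose some power

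*Combined protocol and SAP*

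**What the plan says.** Section 4.4 randomises 1:1, "stratifying by treatment status at time of randomisation and study site". Section 4.5 allocates within those strata by "blocked randomisation in random blocks of 2, 4, or 6". Under this single randomisation, the three time-to-event endpoints are tested in three ways:

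- **OS (12.4, and likewise the synopsis):** "A two-sided log-rank test, stratified by treatment status (on treatment Y/N) and study site". Section 12.4 adds: "Un-stratified log-rank tests will be examined as sensitivity analyses".
- **PFS (12.5):** "A two-sided log-rank test, stratified by treatment status at registration, will be used to assess the effect of the intervention". Site is not named.
- **SSE (12.6):** "a log-rank test will be used to determine if there is a statistically significant difference in the time to SSE between the two groups". Neither factor is named, and the test is not said to be two-sided.

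The PFS Cox model is described as "adjusting for stratification factors and other potential confounding factors". Section 12.6 asks for the same kind of adjustment for SSE, and 12.4 adjusts the OS model for the stratification factor(s). Section 1.5 presents treatment and site as the variables whose proper use makes the population homogeneous in risk of death. The documents give no reason for the three specifications.

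**The concern.** Blocking within strata balances the arms on treatment status and site, so differences between strata no longer contribute to the chance variation of the arm comparison. A log-rank test that ignores the strata still counts that variation in its variance. If the strata differ in risk, the test then runs below its nominal level. Pooling men of different risk also pulls the marginal hazard ratio towards 1. Both effects cost power.

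An influence of the factors on PFS and SSE is plausible. Under 4.5, treatment status separates untreated or stable men from men who have had first-line chemotherapy or are progressing on first-line hormonal agents. Under 11.1, the treating physician determines progression, which includes an indication for new therapy. Under 11.2, SSE includes radiotherapy, surgery or a change of antineoplastic therapy for bone pain. These are local decisions in an open-label trial.

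At stake are some power for two secondary endpoints, and coherence: the p-value and the hazard ratio for one endpoint could fall on different sides of 0.05 because they treat the design factors differently.

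**Working it through.** **The plan's own figure.** The documents give no power or event figure for PFS or SSE. The only design figure is for OS in 12.2: HR 0.78, 80% power, alpha 0.05, control median 33.5 months, 36 months' accrual plus 36 months' minimum follow-up, N = 824.

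- Events (Schoenfeld): 4(1.960 + 0.842)² / (ln 0.78)² = 31.40 / 0.0617 = 509.
- Event probability per arm: 1 − [exp(−36λ) − exp(−72λ)] / (36λ). With λ = ln 2 / 33.5 this is 0.665 in the control arm; with 0.78λ it is 0.576. The mean is 0.6205.
- N = 509 / 0.6205, rounded up, = 821. The Freedman and Lachin-Foulkes versions give 829 and 826. The stated 824 reproduces.

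**Test statistic.** Z = Σ(O − E) / √ΣV, with the sums taken over strata. The unstratified test has one stratum.

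**Simulation inputs.**

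- From the plan: N = 866, 1:1 allocation, blocks of 2/4/6 within site × treatment status, 36 + 36 months, two-sided 5%.
- Assumed: true HR 0.78 (the OS design effect, borrowed); 30% of men in the second treatment stratum; baseline median 15 months (PFS-like), or 50 months with deaths censoring at a 33.5-month median (SSE-like); and the number of sites, treatment-status HR and SD of the site log-hazard shown below.
- There were 3,000 trials per cell. Monte Carlo standard error is about 0.4 points for type I error and 0.5 to 0.9 points for power. The tests are compared on the same simulated data.

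| Setting | Sites | Treatment HR | Site SD |
|---|---|---|---|
| a | 20 | 1.0 | 0 |
| b | 10 | 1.5 | 0.2 |
| c | 30 | 1.5 | 0.2 |
| d | 20 | 2.0 | 0.4 |
| e | 20 | 2.5 | 0.6 |

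**SSE-like** (unstratified / treatment status / both factors):

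| Setting | Events | Type I error, % | Power, % | Change, treatment status | Change, both |
|---|---|---|---|---|---|
| a | 265 | 4.6 / 4.5 / 5.2 | 53.0 / 52.6 / 49.5 | -0.4 | -3.5 |
| b | 269 | 4.7 / 5.0 / 5.3 | 50.4 / 51.0 / 50.2 | +0.6 | -0.2 |
| c | 269 | 5.0 / 5.4 / 5.3 | 50.1 / 51.1 / 47.6 | +1.0 | -2.5 |
| d | 277 | 3.7 / 4.2 / 4.7 | 47.8 / 50.1 / 49.8 | +2.3 | +2.0 |
| e | 286 | 3.5 / 4.2 / 5.4 | 45.5 / 48.9 / 52.2 | +3.4 | +6.7 |

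**PFS-like** (treatment status as planned / both factors):

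| Setting | Events | Type I error, % | Power, % | Change |
|---|---|---|---|---|
| a | 760 | 3.9 / 4.6 | 92.6 / 90.6 | -2.0 |
| b | 752 | 5.5 / 5.5 | 92.3 / 91.5 | -0.8 |
| c | 752 | 4.4 / 4.8 | 91.0 / 89.1 | -1.9 |
| d | 734 | 4.3 / 4.7 | 87.7 / 90.0 | +2.3 |
| e | 712 | 2.9 / 5.0 | 80.1 / 87.0 | +6.9 |

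Single type I cells should not be over-read. The planned PFS test shows 3.9% in setting (a), where no prognostic factor has been left out.

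**Why site can cost power.** Thirty sites × two treatment strata is 60 strata: 866/60 = 14.4 men and, for SSE, 269/60 = 4.5 events each. Once only one arm remains at risk in a stratum, its later events carry no information. With ten sites there are 866/20 = 43.3 men per stratum, and the cost in (b) is under one point.

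**The case against.** The strongest reply is that the consequence is conditional and can reverse. Stratifying by both factors gives lower power than the test as written in three of the five settings, for PFS and for SSE alike, although the smallest differences are within simulation noise. Strong prognostic effects are themselves open to doubt: Section 3.1 admits only men at low or intermediate nomogram risk with ECOG 0-1. Section 1.5 speaks of risk of death, not of progression or skeletal events. The Cox models already use the factors, and 12.6 is silent rather than explicitly unstratified; 12.4 uses that term when it means it. These are secondary endpoints with no stated power target, and the error is in the conservative direction.

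Most of this stands. A reader might infer that both tests are certain to be conservative and to lose power; without site numbers or prognostic strengths, the documents cannot show that. Nor is a wholly unstratified test the yardstick for PFS, since 12.5 already stratifies by treatment status. A reader might also treat SSE as the trial's bone-safety endpoint; Table 1 lists it under efficacy, and pathological fracture is separately an expected adverse event in 13.2.

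The reply does not explain why SSE omits treatment status, or why site is fine enough to stratify OS but not the other two endpoints. Silence in 12.6 still leaves the test open to choice.

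**Conclusion.** The inconsistency is real and unexplained. Its statistical cost is conditional on the omitted factors being prognostic for PFS and SSE.

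- **Treatment status in the SSE test:** adding it changes power by -0.4 to +3.4 points over the settings tried, so it is essentially free.
- **Site:** this is a trade-off. Adding both factors moves the SSE test by about -3.5 to +7 points against the unstratified test. Adding site to the planned PFS test moves it by about -2 to +7 points. Losses arise when sites are many and weakly prognostic; gains arise when sites differ clearly.
- **Type I error:** not inflated. Under the strongest heterogeneity tried, the SSE test without strata runs at 3.5% and the planned PFS test at 2.9%.
- **OS:** unaffected.

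The ranges rest on assumed site numbers, prognostic strengths, stratum share, event rates and a borrowed hazard ratio. They illustrate direction and order of size; they do not predict this trial's power.

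**What to change.** 1. In 12.6, specify a two-sided log-rank test stratified at least by the treatment-status factor as used at randomisation, with the unstratified test as a sensitivity analysis.
2. State one rule for site that covers OS, PFS and SSE: either stratify by site with a fixed rule for pooling small sites, or give the reason why an endpoint is treated differently. The pooling rule must be set without reference to results by arm and must also appear in 12.4.
3. Have the Cox models in 12.4, 12.5 and 12.6 handle the factors in one stated way, so that each hazard ratio matches its test.

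The cost is plan wording only, with no new data and no change to sample size. Item 1 costs essentially no power. If item 2 brings site into the PFS and SSE tests, up to about 2 points (PFS) or 3.5 points (SSE) could be lost in the settings tried if sites hardly differ; pooling small sites is meant to limit that.
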